6.1 Eligibility criteria

To be included in the investigation, the subjects must comply with the eligibility criteria described below.

6.1.1 Inclusion criteria

	ncluded in the investigation a subject must comply e following inclusion criteria:	Justification for inclusion criteria
1.	Has given written informed consent	To ensure that the subject has been given written and oral information regarding the investigation and know enough about the investigation to decide on participation.
2.	Is at least 18 years and have full legal capacity	To meet the Helsinki Declaration
3.	Is female	The product is indicated for use with females
4.	Has a negative urine Multistix dipstick test for erythrocytes (haematuria)	Haematuria could be a sign of blood in urine infection.

6.1.2 Exclusion criteria

subje	ect is not allowed to participate in case he/she:	Justification for exclusion criteria:
1.	Has used an internal urinary catheter or cystoscopy within the past month	To reduce potential contamination from other events non- distinguishable from this study
2.	Has prior history of bladder surgery	To reduce potential bias from other events non-distinguishable from this study
3.	Is symptomatic and/or on medication for overactive bladder	To reduce potential bias from other events non-distinguishable from this study
4.	Has evidence of ongoing, active, symptomatic UTI (assessed by PI, or delegate)	To reduce potential bias from other events non-distinguishable from this study
5.	Is pregnant and/or breast-feeding	To reduce potential bias from other events non-distinguishable from this study
6.	Is participating in other clinical investigations during this investigation	To reduce potential contamination from other events non- distinguishable from this study
7.	Has menstrual bleeding during study period	To reduce bias of the RBC analysis.

6.1.3 Pregnancy and breastfeeding

For female subjects with childbearing potential (they have had at least one period during the last 12 months), a urine pregnancy test will be performed to ensure the subject is not pregnant. The urine pregnancy test will be performed by dipstick at the trial site. Furthermore, the female subjects should not be breastfeeding, when participating in the clinical investigation.

6.2 Subject Recruitment & Screening

The recruitment of potential subjects will commence only when IRB approval is received. Recruitment will occur in the United States at the single-center, American Health Research (AHR). The recruitment period from first subject enrolled to last subject enrolled will be approximately 2 months. The recruitment process will be conducted through site screening and advertisement.

6.2.1 Screening Potential Subjects

If a subject is eligible and interested in participating, then written information about the investigation (subject information) will be provided to the subject to ensure they are given the opportunity to understand what the investigation is about. Subjects will be given plenty of time to have any questions they may have addressed by the investigator, or designee. The subject information provides information to subjects about how to contact the investigator or a representative thereof, or a representative of the sponsor (name, telephone number and e-mail address), if they wish to learn more about the study.

If an eligible subject is interested in participating after they have had time to review the subject information, a screening visit will be arranged. This visit will be done in a quiet room reserved to ensure privacy at the investigator's clinic/office. When arranging the visit, the subject must have received the Information Form and given adequate time to review it. The subject will receive both written and verbal information about the possibility of bringing a companion to the visit and to any possible subsequent visits.

The subject has the right to wait before deciding to participate. If/when the subject decides to participate, he/she will be asked to sign the informed consent form. If a subject so desires, and it is certain that it is understood what the investigation entails, and the relevant forms have been signed, the subject is considered enrolled in the investigation.

The Coloplast clinical manager will have close contact to the site during the recruitment period. The principal investigator, or designee, will notify the clinical manager when a subject is enrolled and all future planned visits.

6.3 Point of Enrollment

A subject is considered enrolled in the investigation when written informed consent is obtained. The expected duration for each subject is described in section 5.8.

6.4 Subject Screening and randomization Failures

Subjects that have signed the informed consent form but fail to comply with the eligibility criteria are considered screening failures. A screening failure can be replaced by a new subject if the new subject can complete the investigation within timelines (before last subject last visit and within visit windows).

6.5 Subject Withdrawal Criteria

The subject can withdraw from the investigation at any time for whatever reason without any consequences for their future treatment outside the clinical investigation. The Investigator may also withdraw a subject from the investigation at any time if s/he judges it to be the subject's interest.

The investigator must withdraw a subject from the investigation due to:

- Noncompliance with the CIP impacting the scientific integrity of the investigation.
- If subject's safety and wellbeing is compromised by further participation.
- A subject will be considered lost to follow-up if at least three documented attempts (i.e., via certified letter) have been made to contact the subject and there is no response. If, after these attempts are made, and there is still no response, the subject will be withdrawn from the clinical investigation.

6.6 Subject Identification and Confidentiality

Subjects will be identified on the electronic CRF (eCRF) and any other document transmitted to the sponsor by the principal investigator, or designee, by a unique identification number (subject number) only.

Data entered on the eCRF are confidential and will only be available to the sponsor (including sponsor delegates), members of data management teams, the statistician, or Medical Advisor and if requested to regulatory authorities.

The principal investigator will maintain, as part of the investigator site file, a list identifying all subjects entered in the clinical investigation (Subject Identification Code and Enrolment List). This list is confidential to all others than the Principal Investigator, or designee at the site.

7 Procedures

7.1 Clinical investigation-related procedures

Before initiation of the clinical investigation, Coloplast must be provided with key personnel signed and dated curricula vitae (not more than two years old) to verify qualifications. Key site personnel are those, who treat or evaluate subject data in the clinical investigation. Coloplast will ensure that all site personnel are trained in the investigation procedures, completion of the eCRFs, procedure for reporting a device deficiency, an adverse event or serious adverse event (how, when, to whom), and who to contact in case of emergency related to the investigational products.

See section **Error! Reference source not found.** for an overview of the clinical investigation-related procedures during subject visits, telephone visits, and at product/baseplate change.

7.2 Subject Visits

7.2.1 Screening/Baseline Visit (Visit 0)

If a potential subject is interested in participating after the first contact, a visit (visit 0) will be arranged in a room reserved to ensure privacy and quiet surroundings at the investigator's clinic/department. When arranging the visit, it will be ensured, that the subject has received the Subject Information Form and given plenty of time to review it. The subject will receive both written and verbal information to ensure that the subject understands what was read and explained and can freely agree to participate in the investigation. The subject will, beforehand, also be informed about the possibility of bringing a companion to any subsequent visits. During the visit, the Principal Investigator or designee will provide oral information about the investigation based on the Subject Information Form. The subject has the right to wait before deciding on participation.

If/when subjects decide to participate, they will be asked to sign the Informed Consent Signature Form. If a subject so desires, and it is certain that it is understood what the investigation entails, and the informed consent form has been signed, the subject is considered enrolled in the investigation. Enrolled subjects are entered in the electronic data capture system and will be randomised to either catheterization with MCH or with 2EC. If a subject is enrolled and does not meet inclusion/exclusion criteria, they will be deemed screen failures and will not be randomized.

It is preferred that Visit 0 and Visit 1 are performed on the same day as the urine sample applied for inclusion or exclusion will also be used to determine RBC and WBC at baseline prior to cystoscopy (see flowchart in Table 7-1).

Once consented, the subject will be allocated a subject number.

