5.1 General

A randomized, single-blinded, parallel study, in which each subject will undergo one catheterization comprising of 6 cycles of filling and emptying the bladder. Each cycle will comprise of filling the bladder with 250mL of saline liquid (50mL/min) through the catheter, followed by bladder emptying through the catheter. The catheter will be rotated during emptying at each occurrence of a flow-stop to release any mucosal suction, with the MHC or 2EC, depending on randomization. To ensure that all catheters are rotated at some point during drainage, every catheter should be rotated after complete emptying. Subjects shall be sitting or standing for the catheterization and filling/emptying cycles to increase the efficiency of drainage.

Upon first insertion of the catheter, the residual volume pre-catheterization will be recorded to ensure minimal residual urine left in the bladder prior to the 6 cycles.

The effect of the micro-hole zone or conventional eyelets on the epithelial and vascular urothelial tissue will be assessed with cystoscopies before and after the catheterization including 6 cycles of filling/emptying/rotating.

One investigator will perform the cystoscopies, catheterizations, and make initial assessments of the cystoscopy images according to a 4-point rating scale as described in 5.3. Two additional investigators will evaluate the endoscopic images post-procedure in a blinded fashion. The evaluations by the 3 investigators will be compared.

The urine at pre- and post-catheterization at Visit 2will be collected for each subject, the total volume noted, and the container will be sent to a local lab for examination of microscopic RBC[1] and WBC results.

Each visit will take approximately 1-2 hours to complete.

Figure 5-1 presents the study overview and Table 7-1 presents the schedule of assessments.

[figure not shown]

Figure 5-1 Study overview

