5.4 Demography and potential compromising factors

The following baseline data will be collected and registered at Visit 1 by the investigator or designee:

- · Date of Informed Consent
- Subject number
- Date of visit
- Age
- · Check of inclusion criteria
- Check of exclusion criteria
- Complete randomization

There are no restrictions. However, concomitant medication should be noted. Prophylactic antibiotics should be provided as one time treatment at first visit.

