7.2.2 Study visits (V1, and V2)

NOTE: All urine volumes (including pre-catheterization residual volumes) will be measured in the same manner throughout the study.

Day 1 (Visit 1):

- Evaluation of Inclusion/Exclusion criteria, including the assessment of any ongoing, active, symptomatic UTI (assessed by Investigator)
- Collection of demographic and baseline data

- Randomisation
- V1-1: A baseline urine sample pre-cystoscopy is collected for the following examination:
 - Dipstick for pregnancy (positive/negative)
 - Dipstick for haematuria (positive/negative)
 - Negative
 - Negative
 - Non-haemolysed 10Ery/ul (+/-)
 - Haemolysed 10Ery/ul (+/-)
 - Positive
 - Non-haemolysed 80 Ery/ul (2+)
 - Haemolysed 25 Ery/ul (1+)
 - Haemolysed 80 Ery/ul (2+)
 - Haemolysed 200 Ery/ul (3+)
- V1-2: The 1st cystoscopy is performed, where the scope is positioned at the centre of the bladder and 6 adjacent images of the dome, posterior wall, and trigone are filmed/photographed to create a naïve bladder map. Cystoscope is inspected for visual blood.
- Collection of concomitant medications. Prophylactic antibiotics should be provided as one time treatment at first visit.
- Collection of adverse events, if applicable

Day 2 (Visit 2):

- V2-1: Urine from a natural void will be collected pre-catheterization. Once the urine sample is obtained, urine volume(mL), RBC and WBC will be evaluated. Haematuria will also be evaluated via dipstick.
- V2-2: Catheterization with either a micro-hole zone- or a 2-eyelet catheter (depending on the randomization). Upon first catheter placement, residual volume pre-catheterization is recorded. Hereafter, the bladder is filled with 250mL (at intervals of 50mL/min) of saline water followed by bladder drainage via the catheter. The catheter is rotated to release any mucosal suction during emptying. Once fully emptied, the catheter is rotated once more to ensure all catheters are being rotated at some point during emptying. The bladder is again filled with 250mL (at intervals of 50mL/min) of saline water followed by bladder drainage and rotations. This procedure is repeated 6 times using the same technique and equipment. The catheter is inspected for visual blood.
- V2-3: The subject will be provided water to drink and the urine from a natural void will be collected.
 Once the urine sample is obtained, urine volume(mL), RBC and WBC will be evaluated Haematuria will also be evaluated via dipstick.

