- V2-4: A 2nd cystoscopy is performed, where the scope is positioned at the centre of the bladder and the same 6 adjacent images of the dome, posterior wall, and trigone are filmed/photographed as during the 1st cystoscopy and a second set of images are obtained. The captured areas are to be carefully selected so they match those in the first set of photographs based on blood vessels and surface features. Cystoscope is inspected for visual blood.
- Collection of any new concomitant medications
- Collection of adverse events and/or device deficiencies, if applicable

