7.4 Schedule of assessments

Table 7-1 Schedule of assessments

	Day 0			Day 2			
Procedures	VO	V1-1	V1-2 (Cystoscopy)	V2- 1	V2-2 (1 catheterization: 6 x repositioning)	V2-3	V2-4 (Cystoscopy)
Informed consent (Allocation of Subject Number in EDC)	x				15	*(
Inclusion/Exclusion criteria	-	X					
Randomization		Х					
Demographics & Baseline Data Collected		x					
Urine sample -Dipstick haematuria -Dipstick pregnancy test (pregnancy test only at V1-1)		x	*	×	e = *	×	
RBC				Х		X	
WBC				Х		X	
Cystoscopy Imaging			Х				X
Bladder Assessment							X
Volume of Urine recorded			a l	x		x	
Pre-catheterization Residual Volume					X		
Visualization of blood	×		X		X		Х
Adverse Events	Х	Χ	Х	Х	X	Х	X
Concomitant Medications	х	х	х	х	X	х	х
Device Deficiencies				7-	X	Х	X

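### Does the RBC and WBC count mentioned before the first cystoscopy, but never scheduled, call for a change to the plan?

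*Combined protocol and SAP*

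**What the plan says.** Section 7.2.1 prefers Visits 0 and 1 on one day because "the urine sample applied for inclusion or exclusion will also be used to determine RBC and WBC at baseline prior to cystoscopy". It refers the reader to Table 7-1 for this.

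The operative text does not carry that count:

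- Section 7.2.2 opens the Visit 1 urine item with "V1-1: A baseline urine sample pre-cystoscopy is collected for the following examination". Only a pregnancy dipstick and a haematuria dipstick follow.
- Section 5.4 introduces the Visit 1 list with "The following baseline data will be collected and registered at Visit 1 by the investigator or designee". The list has no cell counts.
- Section 5.1 describes the laboratory urine as follows: "The urine at pre- and post-catheterization at Visit 2will be collected for each subject, the total volume noted". It mentions no laboratory urine from Visit 1.
- Section 5.2.2 sets both exploratory endpoints at Visit 2.
- Table 7-1 in section 7.4 marks RBC and WBC at V2-1 and V2-3 only. It marks the haematuria dipstick at V1-1, V2-1 and V2-3.

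Section 5.3 describes the exploratory counts as taken on either side of the catheterisation. Section 10.3 gives them descriptive statistics, and section 10 says that summaries are presented by treatment.

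**The concern.** Read against the schedule, 7.2.1 promises a baseline that nobody is told to measure. Every scheduled count comes after the first cystoscopy (V1-2), and instrumentation can itself leave red or white cells in the urine. The plan seems alert to this, since exclusion criterion 1 removes a subject who "Has used an internal urinary catheter or cystoscopy within the past month". Yet V2-1, the count that serves as the pre-catheterisation value, is taken the day after a cystoscopy.

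The same cystoscopy supplies the pre-catheterisation images: "The 1st cystoscopy is performed, where the scope is positioned at the centre of the bladder and 6 adjacent images". The comparison images come from V2-4: "A 2nd cystoscopy is performed, where the scope is positioned at the centre of the bladder". Whatever the first scope leaves behind after its images are captured therefore falls between the two gradings.

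If this mattered, a laboratory value separating the subject's own baseline from the effect of the scope would be lost for each subject and could not be recovered later. A site could also be unsure whether to send the V1-1 urine for counting, section 10 promises that all baseline assessments are reported, and section 13 treats any variance from the protocol as a deviation.

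**Working it through.** No figure in the plan needs reproducing here, so the check is one of sequence and use.

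**1. Order of events (7.2.2 and Table 7-1).** V1-1 urine, dipsticks only → V1-2 first cystoscopy, pre images → V2-1 urine, RBC and WBC → V2-2 catheterisation with six cycles → V2-3 urine, RBC and WBC → V2-4 second cystoscopy, post images.

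**2. Counts before any instrument.** By the schedule, 0 of 2. If 7.2.1 is followed as well, 1 of 3. Table 7-1 agrees with the prose of 5.1, 5.2.2, 5.4 and 7.2.2, so 7.2.1 is the outlier and the mismatch is not an effect of a damaged table.

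**3. What the exploratory endpoints need.** Sections 5.2.2 and 5.3 need a value before and a value after catheterisation at Visit 2. These are V2-1 and V2-3, and the within-subject change is (V2-3) − (V2-1). Only V2-2 lies between them. A V1-1 count does not appear in this expression.

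**4. What the between-arm comparison needs.** Write the change in arm *a* as *c* + τ_a, where *c* is what the first cystoscopy contributes and τ_a is the catheter's contribution. The difference is (*c* + τ_MHC) − (*c* + τ_2EC) = τ_MHC − τ_2EC, so *c* cancels. This takes the effects as additive. Without additivity on a 4-point scale, the arms are still compared fairly, because both receive the same first procedure. A urine count at V1-1 would not alter an image grade in either case.

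**5. Values not obtained if the schedule is followed.** Two counts per subject: 40 × 2 = 80 for 40 completers, and at most 50 × 2 = 100 for 50 enrolled. The second figure is an upper bound, because enrolment is at consent (6.3) and includes screening failures.

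**6. What those values could show.** The change (V2-1) − (V1-1), pooled over arms, would have a 95% half-width of t(0.975, n−1)/√n in units of the SD of the change: 0.320 for n = 40 and 0.468 for one arm of 20. No SD is given, and the plan contains no such analysis. Nor could the change be read as a cystoscopy effect. The one-time prophylactic antibiotic is given at the first visit (5.4, 7.2.2), day-to-day variation falls in the same interval, there is no uninstrumented control, and urine volume is recorded only at V2-1 and V2-3, so dilution at V1-1 would be unknown.

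**7. Exclusion criterion 1.** Its stated justification in 6.1.2 concerns other events that cannot be told apart from this study. It guards against exposure from outside, unevenly spread over subjects. It does not set a standard for a procedure that the protocol itself gives to everyone, so comparing the one-day gap before V2-1 with the one-month window says nothing about bias.

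**The case for a change.** The best case for acting is that the count is cheap now and cannot be recovered later. The urine is already collected, so one extra laboratory test per subject would honour 7.2.1, with no new visit or procedure. The dipstick is a coarse substitute: 7.2.2 classes trace results of 10 Ery/ul as negative, so a subject can enter with some red cells, and nothing measures white cells before the scope. All of that is true, and so is the contradiction.

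The consequences are smaller than they seem:

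- **Deviations.** A site that counts at V1-1 satisfies 7.2.1 and can still complete everything in Table 7-1, since no passage forbids the extra count. Section 11.1.1 confines the CRF to data that the plan mentions, and 7.2.1 mentions this one. Only omission conflicts with a passage. No endpoint needs the value, so on section 13's own definitions omission would be a minor deviation.
- **Reporting.** Section 5.4 lists the baseline data without counts. Section 10 allows summaries or listings and bases N on non-missing data. An analyst would report V1-1 counts if they exist and none if they do not.
- **Naming the change in 10.3.** Section 5.3 already identifies the values before and after catheterisation, and section 10 already gives summaries by treatment. A competent analyst would tabulate V2-1, V2-3 and the change by arm without being told.

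**Conclusion.** The mismatch is a clerical slip: one clause in 7.2.1 was not carried into the schedule, or was left behind when the counts were placed at Visit 2. No change to the plan follows, because neither way of resolving it would alter a result. Deleting the clause is a text edit. Adding the count yields a descriptive value that no endpoint uses and that could not be attributed to the cystoscopy.

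Its size is 80 unscheduled values for 40 completers (at most 100 for 50 enrolled), with no effect on the Visit 2 contrast, the comparison between arms or the primary endpoint. This rests on three points: the first cystoscopy is performed alike in both arms, as 7.2.2 describes; RBC and WBC remain exploratory and descriptive; and V2-1 and V2-3 are obtained as scheduled. If the document is reopened for another reason, 7.2.1 can be brought into line with Table 7-1 at the same time.

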7.2.2 Study visits (V1, and V2)

NOTE: All urine volumes (including pre-catheterization residual volumes) will be measured in the same manner throughout the study.

Day 1 (Visit 1):

- Evaluation of Inclusion/Exclusion criteria, including the assessment of any ongoing, active, symptomatic UTI (assessed by Investigator)
- Collection of demographic and baseline data

- Randomisation
- V1-1: A baseline urine sample pre-cystoscopy is collected for the following examination:
 - Dipstick for pregnancy (positive/negative)
 - Dipstick for haematuria (positive/negative)
 - Negative
 - Negative
 - Non-haemolysed 10Ery/ul (+/-)
 - Haemolysed 10Ery/ul (+/-)
 - Positive
 - Non-haemolysed 80 Ery/ul (2+)
 - Haemolysed 25 Ery/ul (1+)
 - Haemolysed 80 Ery/ul (2+)
 - Haemolysed 200 Ery/ul (3+)
- V1-2: The 1st cystoscopy is performed, where the scope is positioned at the centre of the bladder and 6 adjacent images of the dome, posterior wall, and trigone are filmed/photographed to create a naïve bladder map. Cystoscope is inspected for visual blood.
- Collection of concomitant medications. Prophylactic antibiotics should be provided as one time treatment at first visit.
- Collection of adverse events, if applicable

Day 2 (Visit 2):

- V2-1: Urine from a natural void will be collected pre-catheterization. Once the urine sample is obtained, urine volume(mL), RBC and WBC will be evaluated. Haematuria will also be evaluated via dipstick.
- V2-2: Catheterization with either a micro-hole zone- or a 2-eyelet catheter (depending on the randomization). Upon first catheter placement, residual volume pre-catheterization is recorded. Hereafter, the bladder is filled with 250mL (at intervals of 50mL/min) of saline water followed by bladder drainage via the catheter. The catheter is rotated to release any mucosal suction during emptying. Once fully emptied, the catheter is rotated once more to ensure all catheters are being rotated at some point during emptying. The bladder is again filled with 250mL (at intervals of 50mL/min) of saline water followed by bladder drainage and rotations. This procedure is repeated 6 times using the same technique and equipment. The catheter is inspected for visual blood.
- V2-3: The subject will be provided water to drink and the urine from a natural void will be collected.
 Once the urine sample is obtained, urine volume(mL), RBC and WBC will be evaluated Haematuria will also be evaluated via dipstick.
- V2-4: A 2nd cystoscopy is performed, where the scope is positioned at the centre of the bladder and the same 6 adjacent images of the dome, posterior wall, and trigone are filmed/photographed as during the 1st cystoscopy and a second set of images are obtained. The captured areas are to be carefully selected so they match those in the first set of photographs based on blood vessels and surface features. Cystoscope is inspected for visual blood.
- Collection of any new concomitant medications
- Collection of adverse events and/or device deficiencies, if applicable

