10.1 Definition of analysis populations

Intention to Treat (ITT), Safety and Per Protocol (PP) populations will be defined at a formal data review meeting before database lock. As a minimum, the data manager, the clinical manager and the statistician will be involved in the classification of subjects.

The Safety population (basis for the AE summary) will include subjects with valid informed consent.

The ITT population (Full analysis set) will be constituted by all randomized subjects, with valid informed consent, who have been exposed to at least one product, and with recorded information on at least one endpoint (non-missing).

Due to the explorative nature of this investigation, no formal PP population is planned. However, if deemed necessary, a PP population will be established, based on a subset of the ITT population.

Individual endpoints/data points may be excluded from analysis, even though the corresponding subject belongs to the ITT and/or PP population. Any exclusion of subjects or data points from any of the populations must be documented.

All analyses will be based upon the ITT population and AEs will be summarized based on the safety population.

The Safety population will include all subjects who have given informed consent.

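### Randomisation is placed at Visit 1, before the baseline cystoscopy, although the allocated catheter is first used on Day 2; moving it to just before V2-2 would cheaply avoid exclusions after randomisation

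*Combined protocol and SAP*

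**What the plan says.** **Time of randomisation.** Section 7.2.2 lists it under Day 1 (Visit 1), above the V1-1 urine sample and above the baseline imaging: "V1-2: The 1st cystoscopy is performed, where the scope is positioned at the centre of the bladder". In section 7.4, "Table 7-1 Schedule of assessments" marks it in the V1-1 column, the same column as the eligibility check and the dipsticks. Section 5.4 includes it in a list without an order, introduced by "The following baseline data will be collected and registered at Visit 1 by the investigator or designee". Section 7.2.1 mentions it under Visit 0: "Enrolled subjects are entered in the electronic data capture system and will be randomised to either catheterization with MCH or with 2EC". The sentence after that says subjects who fail the criteria are screen failures and are not randomised.

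**First use of the device.** Section 7.2.2, Day 2: "V2-2: Catheterization with either a micro-hole zone- or a 2-eyelet catheter (depending on the randomization". Section 4.8 allows one catheterisation per subject, so nobody is exposed before V2-2.

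**Analysis set.** Section 10.1 limits the ITT set, which it also calls the full analysis set, to randomised, consented subjects "who have been exposed to at least one product, and with recorded information on at least one endpoint (non-missing". All analyses except the adverse event summary use this set. The section adds: "Any exclusion of subjects or data points from any of the populations must be documented".

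**Withdrawal.** Section 6.5: "The subject can withdraw from the investigation at any time for whatever reason". The investigator may also withdraw a subject on judgement.

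**Who knows the arm.** Under section 5.1 one investigator does the cystoscopies and catheterisations and makes the first grading. Section 5.7 blinds the two image reviewers and, until database lock, the statistician. Section 5.6 makes randomisation central but does not say when the arm is shown to the site.

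**The concern.** Nothing done before V2-2 depends on the arm, yet the arm is assigned at the previous visit. Three things follow.

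First, the baseline cystoscopy and the return for Visit 2 fall between assignment and exposure. A subject who leaves in that window has been randomised but is not in the efficacy set. If the reason is connected with the arm, the comparison is no longer fully protected by randomisation.

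Second, the baseline fields may be captured by someone who knows the arm. V2-4 has to reproduce the V1-2 fields, and all three graders compare paired images of those fields. The choice at V1-2 therefore settles where change can be seen, and blinded grading cannot correct that choice afterwards.

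Third, the order of the 7.2.2 list puts randomisation ahead of the haematuria and pregnancy dipsticks. This does not fit the rule in 7.2.1 that ineligible subjects are not randomised. Table 7-1 does not settle the order, because all these items share one column.

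**Working it through.** **The plan's own figure.** Section 6 asks for 50 enrolled so that 40 complete at 20% drop-out: 40 / (1 − 0.20) = 50. It reproduces. The 40 cannot be derived, because section 10.4 gives no effect size, SD or power.

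**How many could leave the set before exposure.** The plan allows for 50 − 40 = 10 losses but does not say when they occur. Suppose all 50 are randomised at Visit 1 and a share f of the 10 falls before V2-2 (f is an assumption).

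| f | Randomised but outside the ITT set | Share kept | Number to randomise if done just before V2-2 |
|---|---|---|---|
| 0 | 0 | 50/50 = 100% | 50 |
| 0.5 | 5 | 45/50 = 90% | 45 |
| 1 | 10 | 40/50 = 80% | 40 |

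Enrolment stays at 50 in every row. The 10 is an upper limit at the planned drop-out, not a forecast: enrolment is counted from consent (section 6.3), so some of the 20% may be screening failures. A urine result from V2-1 would not bring a lost subject back into the set, because exposure is also required.

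**Bias if loss is related to arm.** Let n be the number randomised to an arm, L the number lost from it, and d the difference in mean grade change between those lost and those kept. The mean of the kept subjects differs from the mean of all n by L·d/n. L, d and the SD are assumptions. An equal split of 40 to 50 subjects gives n = 20 to 25.

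| n | L | Shift, d = 0.5 | Shift, d = 1 | SE, SD 0.5 | SE, SD 1.0 |
|---|---|---|---|---|---|
| 25 | 1 | 0.020 | 0.040 | 0.143 | 0.286 |
| 25 | 2 | 0.040 | 0.080 | 0.144 | 0.289 |
| 20 | 1 | 0.025 | 0.050 | 0.160 | 0.320 |
| 20 | 2 | 0.050 | 0.100 | 0.162 | 0.325 |

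Here SE = SD·√(1/n + 1/(n − L)). Relative to the SE, the shift runs from 0.020/0.286 = 0.07 to 0.100/0.162 = 0.62.

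**Unequal arms.** The synopsis asks for at least 20 per product within 50, and section 5.6 gives no ratio, so one arm could reach 30. For losses from an arm of 30, the shift runs from 1 × 0.5/30 = 0.017 to 2 × 1/30 = 0.067 grade. For 2 losses from an arm of 20 against 30, SE = 0.5·√(1/30 + 1/18) = 0.149, and 0.100/0.149 = 0.67. The range of about 0.02 to 0.10 grade stands.

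**Extreme case.** With L = 5 in one arm, the shift runs from 5 × 0.5/25 = 0.10 to 5 × 1/20 = 0.25 grade. That is 0.10/0.300 = 0.33 to 0.25/0.171 = 1.46 standard errors. Five losses from one arm over about a day is unlikely.

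**Precision.** For arms of a and b, imbalance alone multiplies the SE by 1/√(4ab/(a + b)²): 1.0014 at 20 v 18 and 1.033 at 25 v 15. This is negligible.

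**The case against.** The study is exploratory, with no pass/fail criterion (10.6). The exposure condition is stated openly, exclusions must be documented, and a lost subject stays in the safety set. She has no post-catheterisation image, so renaming the set or keeping her in it would change no primary estimate. All of that stands. It is why the remedy is to move randomisation rather than to relabel the set.

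A reader might infer that subjects know their arm at Visit 1 and leave because of it. The documents do not support this. Section 5.7 leaves subjects unblinded because the products look different, but no section shows a product to a subject, or tells her the arm, before V2-2. No section assigns any of the 20% drop-out to this interval.

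A reader might also infer that the operator steers the baseline fields by arm. Section 5.6 is silent on when the arm is seen, and silence is not disclosure. V1-2 is a standard map of six adjacent images over named regions. To exploit it, the operator would have to predict where lesions will later appear. What remains is some latitude within those regions and no rule that withholds the arm.

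Bullet order is weak evidence of chronology, since a literal reading conflicts with 7.2.1, and the study overview figure is not available here. Table 7-1, however, independently puts randomisation in the column before V1-2. Any reading of 5.4, 7.2.1, 7.2.2 and Table 7-1 leaves randomisation at least one visit ahead of first use.

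**Conclusion.** The point holds as an avoidable weakness of sequence. A randomised subject lost before V2-2 is excluded from every efficacy analysis. The arm is not withheld from the operator at V1-2. The listed order is inconsistent with the rule on ineligible subjects.

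The expected effect is small. It is zero if loss is unrelated to arm, and about 0.02 to 0.10 grade (roughly 0.07 to 0.62 standard errors with equal arms) for 1 to 2 losses from one arm. These figures rest on assumed values for the number lost, their difference in grade and the SD; the documents give none of them. Neither arm-related loss nor arm-influenced choice of fields is shown. The case for change rests on its low cost, not on a large effect.

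**What to change.** In sections 5.4, 7.2.1, 7.2.2 and Table 7-1, state a single randomisation point: Visit 2, immediately before V2-2, after eligibility is confirmed and the V1-2 images have been captured. Capture is enough; no image-upload deadline is needed. In section 10.1, add that any randomised-but-not-catheterised subjects will be reported by arm.

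If randomisation has to stay at Visit 1, withholding the arm until V2-2 would protect baseline capture equally and leave no route from arm to early loss. The exclusions themselves would remain.

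Cost: one EDC form moves, a few sections are reworded, and both devices must be on hand at Visit 2. Enrolment stays at 50. The change does not blind the operator at V2-2 or V2-4, where the same person matches the fields after using the catheter, and it does not prevent losses after V2-2.
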